5.0 Procedures Involved

5.1 Study Design:

Mixed methods is generally defined as the collection and analysis of both quantitative and qualitative data that links these two forms of data concurrently, sequentially, or embedded one into another.^{57,58} Among the various rationales for conducting mixed methods research are: a) to better understand a research problem by converging numeric trends from quantitative data and specific details from qualitative data; and b) to obtain statistical, quantitative data from a sample of a population and use them to identify individuals who may expand on the empirical results through qualitative findings.⁵⁹ Few evaluations of ADRD caregiver interventions have combined qualitative and quantitative data to obtain a greater understanding of why certain protocols are beneficial or not. For these reasons, an embedded experimental mixed methods design will be utilized for the proposed demonstration. An embedded experimental mixed methods design combines the collection and analysis of qualitative data within a traditional randomized controlled trial (RCT) design; the collection of the embedded qualitative data may occur prior to, during, or after the

RCT.^{57, p. 90} The embedded experimental design will assist the research team examine the process of eNeighbor's implementation during the conduct of the RCT and determine why and how the eNeighbor worked or did not for ADRD caregivers following the completion of the RCT (see Figure 1).^{57,60-63}

5.2 Study Procedures:

Recruitment. The Principal Investigator (PI) or research coordinators (RCs) will initiate email, telephone, or mail contact with ADRD caregivers on the University of Minnesota Caregiver Registry (IRB# 1007S85812) or others recruited by the PI (see above) who potentially meet the project inclusion criteria. In addition, the PI or RCs will ask professional caregivers on the Registry to identify potential ADRD caregivers for recruitment purposes (this will also occur via the various other recruitment and outreach activities noted above). During initial enrollment contacts, the PI or RCs will describe the eNeighbor monitoring system, explain study procedures, and invite potential ADRD caregivers to participate. Caregivers will be offered the opportunity to ask any questions about the study procedures. The Telephone and Email script will be utilized. =

These recruitment efforts will be facilitated by the Minnesota Board on Aging (MBA), the Minnesota-North Dakota Alzheimer's Association regional office, and other organizations. The MBA will help us promote this study through Area Agencies on Aging, many of which serve ethnic and racially diverse older adults as well rural ADRD caregivers. Specifically, the Information Sheet will be distributed to the MBA and associated Area Agencies on Aging in Minnesota, the Minnesota-North Dakota Alzheimer's Association, or other organizations to distribute to family members or family members of clients that these organizations serve. The Information Sheet is also used as the basis for any other advertising efforts or by other organizations who wish to reach out to their clients and families regarding this opportunity. Finally, a Letter to Families can be sent to organizations if they wish to distribute to their clients or family members of clients.

Additional recruitment efforts may occur, on an as-needed basis, via the PI's or RC's community outreach efforts. The PI, via the annual Caring for a Person with Memory Loss conference (see <https://www.sph.umn.edu/events-calendar/caring-for-person-with-memory-loss-conference/>) and a number of other community presentations, will have the opportunity to recruit potential participants. Following an overview of the study procedures, the PI or RC will provide interested participants with a Documentation of Permission form to complete, which will provide the PI and research team members to contact the potential participant to determine eligibility and proceed with enrollment. If independent living settings or similar residential providers are willing to collaborate with the research team to identify potential participants, we ask them to: a) distribute via email or print the study flyer, information sheet, letter to families, and/or other recruitment information to announce the study and its availability; b) approach residents or family members to discuss the study, and if there is interest, obtain permission for [name] or his team to follow-up and contact them to initiate the recruitment and enrollment procedure; and c) setting liaisons will simply forward potentially interested family members' contact information to [name] to do so.

Eligibility screening. If caregivers agree to participate, the PI or RC will initiate a brief screening procedure. The following inclusion criteria will be applied for persons with ADRD: 1) English speaking; 2) physician diagnosis or recognition of ADRD (e.g., Alzheimer's disease, Lewy Body disease, fronto-temporal dementia, or stroke/vascular dementia; mild cognitive impairment); 3) not currently receiving care or case management services; and 4) 55 years of age and over.

PROTOCOL TITLE: A Proactive Health Monitoring Intervention for Dementia Caregivers: The eNeighbor

Caregivers of persons with ADRD must: 1) speak English; 2) be 21 years of age and over; 3) self-identify as someone who provides help to the person with ADRD because of their cognitive impairments; 4) self-identify as the person most responsible for providing hands-on care to the person with ADRD or sharing that role with someone else (i.e., the “primary” family caregiver, which can include highly involved kin or non-kin of persons with ADRD; those who share care responsibilities are also eligible); 5) plan to, or ideally wish to, remain in the area for at least 18 months in order to reduce possible loss to follow-up; and 6) indicate a willingness and need to use eNeighbor. To determine eligibility, the E-Neighbor Screening Form will be administered either in-person over the telephone by the PI or RC to determine and identify eligible persons with ADRD and their family caregivers.

Enrollment/Consent and Assent

Within two weeks following the completion of eligibility screening, consent/assent procedures and baseline interviews will be scheduled within 2 weeks for eligible caregivers. Signed informed consent from the eligible family caregiver will take place. Signed informed consent will be offered in-person, via mail, or if deemed most convenient to the family caregiver, via an online consent form.

If a legally authorized representative (LAR) for the person with ADRD is identified other than the family caregiver, we will also obtain signed consent from this individual. For the purposes of efficiency, we will offer an online consent form to review and approve. All online consent and HIPAA forms will be administered via the secure University of Minnesota Google Docs application.

In addition to administering informed consent forms to family caregivers and LARs, we will additionally provide HIPAA forms (either in-person or via mail and online formats) for the family caregiver and LAR to review and sign. To complete this procedure, the Family Caregiver Consent Form, the LAR Consent Form, and the HIPAA form will be utilized.

Following the securing of consent of primary caregivers and LARs, Verbal Assent of persons with ADRD will take place (see supplemental documents uploaded to IRB). While ideally this may take place simultaneously with the consent procedures above, there may be a delay in time (hopefully no more than several days) between when consent is secured from family caregivers and LARs and assent of the person with ADRD.

Baseline

As soon as possible following the completion of consent, HIPAA, and verbal assent, the baseline survey/interview will take place. The survey/interview will ask the family caregiver to complete a survey that will ask questions about the family caregiver, the person with ADRD, and the person with ADRD’s and family caregiver’s memory loss’ emotional, psychological, physical health, the caregiver’s confidence about their care situation. The survey/interview we will also ask the family caregiver about various health events that the person with ADRD may have experienced. The baseline survey can occur in-person, in the family caregiver’s home, Mayo Building at the

PROTOCOL TITLE: A Proactive Health Monitoring Intervention for Dementia Caregivers: The eNeighbor

University of Minnesota, or another location of the family caregiver's choosing. A mail survey, telephone interview, or online survey will also be arranged if that is easier for the family caregiver. If the caregiver elects to complete the online version of the survey, the survey link will be emailed to the caregiver. To complete this procedure, the Baseline eNeighbor Survey will be utilized.

Treatment/Intervention Period

Following the completion of baseline interviews, ADRD caregivers will be randomly assigned to an eNeighbor treatment condition that receives the multi-sensor, remote monitoring system or an attention control group. Randomization (participant is assigned to either the treatment or control condition) will be completed via an a priori list generated from <http://randomizer.org> by the PI. The PI will inform the ADRD caregiver of their randomization status within 2-3 days following completion of the baseline interviews.

The PI or research coordinators will call caregivers in the control group 48 hours following assignment to the usual care control group to address any questions they may have and to thank them for being part of the study and volunteering their time if no response from the participant in the usual care group is received following randomization). Group allocation (either attention control or treatment condition) will be based solely on their a priori randomization assignment number. The PI or research coordinators will then inform the ADRD caregiver of her/his group assignment within 2 days of baseline survey completion.

Following ADRD caregivers' enrollment into the proposed project and within 2 weeks of randomization to the eNeighbor treatment condition, the Director of Nursing and Technology (DNT) will schedule a visit at the home of the person with ADRD and the enrolled family caregiver. The DNT will oversee all system maintenance (battery changes, troubleshoot in instances where there is a loss of system contact), establish arrangements for other care services that are needed for the person with ADRD in instances of eNeighbor alerts or other health-related transitions, and develop and monitor a care plan with the family caregiver to ensure that it is effectively followed.

An initial Needs Assessment takes place to determine the best use and deployment of the eNeighbor remote sensor technology in the person with ADRD's home. The assessment begins with an identification of risk factors that suggest the need for remote health monitoring (e.g., the person with ADRD lives alone and has little supervision; the caregiver needs support; the person with ADRD has a history of falls or the caregiver has concerns with falls) as well as the use of other monitoring systems such as Safe Return™ or a similar device. The DNT will then discuss the results of the needs assessment with the ADRD caregiver and review how the remote monitoring system works, that the eNeighbor does not include cameras or microphones, is secure, and is private, and that the system learns the normal activities of the person with ADRD and alerts both the family caregiver and the DNT if something appears unusual (e.g., absence of expected ADL behaviors). Following this operational overview, the DNT will summarize the secure and password-protected MyHealthsense website, which is used by the family caregiver or other

PROTOCOL TITLE: A Proactive Health Monitoring Intervention for Dementia Caregivers: The eNeighbor

trusted family members and friends to coordinate and share information regarding appointments or the well-being of the person with ADRD. The remote monitoring system will then be installed in the person with ADRD's home and the expected performance thresholds and daily routines will be programmed. The DNT will monitor sensor performance throughout the duration of the project, and if these sensors are damaged or become inoperable, she will replace these sensors as needed free of charge.

A particularly important aspect of eNeighbor is its configuration in homes with varying broadband internet service. If broadband services are available at the person with ADRD's home, connection of the sensors involves the simple addition of a wireless router which connects with the existing broadband modem in the person with ADRD's home (and is included in the remote sensor package that will be supported by the proposed project). If broadband is not available, the current project will support connectivity for the person with ADRD's home via purchase of this service as a "bundle" through an existing telephone or cable TV plan. In the instance the family caregiver does not wish to utilize broadband service options for the purposes of eNeighbor, the proposed project will support a low data rate cellular service plan that supports only eNeighbor functions. The quality of data collection is identical across cellular or broadband modalities. The DNT will then share paper versions of the alert system reports generated by the MyHealthsense website.

To address environmental diversity, the DNT will collect information on the approximate square footage of the house; number of bedrooms and bathrooms; distances between primary bathroom (e.g., the one used to shower/bathe in), living room area (e.g., where television or the majority of similar leisure activity takes place), and entryway; and number of levels in the home.

The Needs Assessment form and utilization data collected by the DNT based on the Healthsense/eNeighbor remote health sensor system will be securely transferred to [name] and RC via a secure University of Minnesota Box file transfer procedure. Any hard copy Needs Assessment forms or similar utilization data will be maintained in a locked file cabinet at The Lutheran Home Association. As one of the analyses proposed will focus on the individualization/customization of the eNeighbor system for each family as well as variable utilization data based on the alerts issued by the remote monitoring system and follow-up contacts by the DNT, these utilization data will be collected throughout the 18-month evaluation period for each caregiver and person with ADRD.

5.3 Follow-Up:

Follow-up will continue until Month 55, resulting in a 53-month data collection period. Eligible ADRD caregivers will be interviewed/surveyed at baseline and every 6 months thereafter for up to 18 months. Six-month follow-up interviews/surveys will be completed by the PI or research coordinators for all participants in the treatment and control conditions. The selected measures have strong psychometric properties, sensitivity to change, and clinical relevance in the evaluation of remote health monitoring technology as established in the stress process and

PROTOCOL TITLE: A Proactive Health Monitoring Intervention for Dementia Caregivers: The eNeighbor

related conceptual models. Caregivers will complete the proposed measures at each time point (context of care items will be collected at baseline only). Baseline and follow-up interviews will take place at a location and in a format that is convenient to ADRD caregivers (at the University of Minnesota Delaware Clinical Research Unit, the ADRD caregivers' home or through online, telephone or mail formats if desired). Each follow-up interview is expected to take approximately 45 minutes to complete. Information from the follow-up surveys will also be utilized to complete the E-Neighbor Disposition Form at each follow-up interval. As the information on the Disposition form is available from the follow-up surveys, the PI or RCs can extract and complete the Disposition form following the completion each 6-, 12-, and 18-month survey.

In general, a call will be placed to every participant near the time when the survey is sent out. For participants who are a part of the control group, this call will serve as a time to check-in, and also make these participants feel connected to the research study. A monthly check-in call/attempt will be placed to those in the eNeighbor treatment group, as a means to confirm that the eNeighbor sensor system is functioning properly.

Furthermore, we will administer a verbal permission/modified assent procedure prior to or following each 6-month interview/survey (i.e., 6 months, and 12 months) for those in the eNeighbor treatment group (unless care recipient passed, moved to a care facility, had sensor system removed).

The rationale for this approach is that since persons with dementia in the control group do not engage in any way with the research procedures or researchers themselves following baseline (i.e., family caregivers complete all surveys), assent is likely not needed in such circumstances as participants in the control group are essentially participating in a family caregiving study. As persons with memory loss in the treatment condition are experiencing the installation and operation of the eNeighbor remote monitoring system in their homes, ongoing permission is necessary for these individuals for the duration of the study follow-up period (i.e., 6 months, and 12 months; note: by the 18-month follow-up surveys/interviews the study procedures are complete and no further assent is needed).

Specifically, verbal assent of persons with Alzheimer's disease or a related dementia (ADRD) (oral only) will take place for those in the eNeighbor treatment condition over the telephone (unless the family caregiver has requested an in-person interview). Family caregivers may also (and are encouraged to) join the telephone call via a conference connection, another land line, or speaker phone to help facilitate the assent process and effectively communicate with the person with memory loss if needed. If a dissenting behavior or agitation is exhibited by the person with memory loss, a conversation with the caregiver alone should take place, to determine if this behavior related to the eNeighbor system is common. If it is common, then the verbal dissent should be noted and the DNT should be contacted immediately to schedule removal of the sensor technology. This will also occur after any adverse/negative reaction to the eNeighbor remote monitoring system.

PROTOCOL TITLE: A Proactive Health Monitoring Intervention for Dementia Caregivers: The eNeighbor

When calling, the staff will defer to caregiver preference in circumstances where the caregiver prefers to provide permission for follow up instead of staff speaking with the care recipient directly either due to severity of memory loss issues (e.g., the care recipient does not remember that the sensors are even in the home) or for another reason. In these circumstances, the staff will ask the caregiver if the caregiver and/or care recipient are still agreeable to continue their participation in the study and use of the sensor system. If they agree, staff will sign a follow-up assent/permission form, thus providing permission for continuation of study procedures (e.g. sensor system use). While the staff is available for any questions that may come up during the call, the full assent form is not read over the phone during these follow-up permission calls.

Several steps will enhance retention in the proposed study. The research coordinator or PI will complete confirmation calls or emails 1-4 days prior to a scheduled interview or survey, will contact ADRD caregivers within 24 hours of a missed interview to reschedule, and will update participants' contact information as needed throughout the project. For those in the eNeighbor treatment condition, the DNT will contact the caregiver 3-4 days following the installation of sensors to ensure the system is operating appropriately and to troubleshoot any issues. In addition, the DNT will follow-up with treatment participants on a monthly basis to further monitor the overall operation of the eNeighbor sensor system, address issues/concerns of the caregiver, and troubleshoot any issues related to the remote health monitoring system.

We will take several steps to address attrition bias. If a person with ADRD has moved into a residential long-term care facility or has died, caregiver follow-up interviews will include queries determining when these events occurred. Regular follow-up will continue in order to collect as much information on outcome variables that are appropriate (i.e., intention to treat principle). Per the consent form, participants will have the opportunity to provide a Social Security Number for the care recipient to study staff (over the phone) during/at the end of the study. Participants may also choose to opt out of this. At the conclusion of the project, Thank You cards will be mailed to all participants to ensure rapport.

Treatment fidelity. Monthly system reviews will take place through system reports generated by the Director of Nursing and Technology. The MyHealthsense portal can also track how often the ADRD caregiver or others utilize the care coordination resources of MyHealthsense. The PI or research coordinator will also determine the degree to which participants apply the eNeighbor monitoring tool to their everyday care situations. An online or mail survey of close-ended, Likert-scale items to determine eNeighbor's acceptability by ADRD caregivers as well as multiple open-ended questions will be administered to all ADRD caregivers in the eNeighbor treatment condition at the 6-, 12-, and 18-month interview intervals. The open-ended responses will provide qualitative data as to the reasons why family caregivers felt the health monitoring technology of eNeighbor was or was not easy to utilize (e.g., "Why or how was the health monitoring technology easy or difficult to use?" The identification of these barriers or facilitators will be considered when examining ADRD caregivers' perceptions of eNeighbor's design, delivery, and ease of use.

Final Study Visit/Survey.

The final study visit will operate similar to the other follow-up interviews/surveys. Following completion of the final 18-month assessment, participants in the treatment group will be informed of the conclusion of the study and the need to remove the health monitoring sensors. However, available eNeighbor sensor packages purchased for this demonstration project will also be offered to the control group on a first-come, first-serve basis at the conclusion of the randomized control trial evaluation phase as stated in the consent form. If the eNeighbor system is found to have an overall negative effect (specifically, the eNeighbor system results in greater emotional stress or depressive symptoms on the part of the caregiver) then the eNeighbor system will not be offered on a first-come, first-serve basis for those in the control group. The latter is now included to provide additional clarification in the consent form. For those not selected but who desire the health monitoring technology, the project team will work with HealthSense to determine if discounts are available and applicable.

Post-evaluation semi-structured interviews. Thirty semi-structured interviews with ADRD caregivers in the e-Neighbor treatment condition will take place. These interviews will take place a month after completion of the final 18-month follow-up interview for selected participants. The PI and [name] (the Co-I) will identify 15 ADRD caregivers who indicated positive acceptance on the embedded qualitative and quantitative 6-, 12-, and 18-month system reviews and 15 ADRD caregivers who reported low acceptance on the embedded qualitative and quantitative 6-, 12-, and 18-month system reviews.

A stratified purposive sampling approach will also be applied; the PI and [name] will purposively identify ADRD caregivers of varying kin relationship (spouse vs. adult child), dementia severity (middle versus late stage dementia symptomatology), caregiver gender, and racial or ethnic background to participate in the post-RCT semi-structured interviews.

The open-ended responses of the semi-structured interviews will provide in-depth information on the reasons why dementia caregivers felt the eNeighbor remote sensor technology did or did not reduce ADRD caregivers' distress, help to manage persons' with ADRD daily function, or prevent negative health transitions and service use for persons with ADRD. The PI and research coordinators will schedule and conduct the semi-structured interviews and will digitally record each interview. Audio recordings will be transcribed by a professional transcriptionist into a Microsoft Word® file which will then be uploaded to nVivo for subsequent analysis.

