9.0 Study Population

9.1 Inclusion Criteria:

The following inclusion criteria will be applied for 200 persons with ADRD: 1) English speaking; 2) physician diagnosis of ADRD (Alzheimer's disease, Lewy Body disease, fronto-temporal dementia, or stroke/vascular dementia; mild cognitive impairment only); 3) not currently receiving care or case management services; and 4) 55 years of age and over. Caregivers of persons with ADRD must: 1) speak English; 2) be 21 years of age and over; 3) self-identify as someone who provides help to the person with ADRD because of their cognitive impairments; 4) self-identify as the person most responsible for providing hands-on care to the person with ADRD; 5) plan to remain in the area for at least 18 months in order to reduce possible loss to follow-up; and 6) indicate a willingness to use eNeighbor.

9.2 Exclusion Criteria: Anyone who does not fit the inclusion criteria will be excluded.

9.3 Screening: If caregivers agree to participate, the PI or research coordinators will initiate a brief screening procedure applying the inclusion criteria above.

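### The 18-month residence criterion binds the caregiver, not the person with ADRD whose home holds the sensors, so a family with a move already arranged can be randomised

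*Combined protocol and SAP*

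**What the plan says.** Both eligibility lists place the 18-month requirement among the caregiver criteria. Section 5.2 (Eligibility screening) asks the caregiver to "plan to, or ideally wish to, remain in the area for at least 18 months in order to reduce possible loss to follow-up". Section 9.1 is firmer: "plan to remain in the area for at least 18 months in order to reduce possible loss to follow-up". Both give loss to follow-up as the reason.

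The person with ADRD has four criteria: English, a diagnosis, and "3) not currently receiving care or case management services; and 4) 55 years of age and over". None looks ahead to where that person will live. Section 9.2 adds nothing: "Anyone who does not fit the inclusion criteria will be excluded". The nearest safeguard is caregiver criterion 6 in 5.2, "6) indicate a willingness and need to use eNeighbor"; section 9.1 keeps the willingness and drops the need.

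On follow-up, section 5.3 lets caregivers answer "through online, telephone or mail formats if desired". In the treatment arm, permission for continued sensor use is renewed at 6 and 12 months "unless care recipient passed, moved to a care facility, had sensor system removed". Section 5.2 puts the sensors in the home of the person with ADRD and places the Needs Assessment after randomisation. Section 5.3 keeps families in follow-up after a move to residential care, citing intention to treat. Section 17.3 makes time to nursing home admission, defined by a stay of at least 90 days, a Cox outcome for Hypothesis 3.

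**The concern.** The criterion protects the part of the design that is less at risk. A caregiver who leaves the area can still be surveyed. Exposure to eNeighbor depends on the person with ADRD staying in the equipped home, and no criterion addresses that. A family that has accepted a facility place or fixed a moving date meets every listed requirement in 9.1.

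Two analyses are affected. For the primary outcomes (self-efficacy and competence), such a treated family has a shortened exposure and still counts in full under intention to treat. In the nursing home admission model, placements settled before randomisation occur in both arms whatever the allocation and pull the hazard ratio towards 1. Placements that arise after randomisation are legitimate outcomes and are not at issue. Because intention to treat rightly keeps these families in, the only clean place to deal with them is before randomisation.

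**Working it through.** **Inputs from the documents.** 100 per arm (1.0); 0.50 SD, power .80, p < .05 and 20% attrition (17.2); 18 months of follow-up (5.3).

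**Inputs assumed.** Two-sided test. A share q of families with a move already arranged, equal in both arms and among completers, gaining nothing. For placement: 25% of other controls admitted by 18 months, true hazard ratio 0.60, exponential times, and arranged placements spread over months 0–4 in both arms. The documents supply none of these.

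**Step 1: the plan's own figure.** n per arm = 2 × (1.96 + 0.842)² / 0.50² = 62.8, so 63 (64 with the t distribution). That is 126–128 completers, or 158–160 enrolled after dividing by 0.80. The plan enrols 200 and calls that sufficient. It leaves 200 × 0.80 = 160 completers, 80 per arm, and power Φ(0.50 × √40 − 1.96) = Φ(1.20) = 0.885 (0.882 by the t test). The claim of sufficiency is confirmed, with some slack.

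**Step 2: dilution of the mean difference.** The effect becomes 0.50 × (1 − q). The smallest effect with 80% power at 80 per arm is 2.80 × √(2/80) = 0.443 SD, so power reaches .80 at q = 1 − 0.443/0.50 = 11.4%, or about 11%.

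**Step 3: placement.** The control cumulative hazard at 18 months is −ln 0.75 = 0.288, and the treated one is 0.60 × 0.288 = 0.173. If every arranged move is a qualifying admission, each arm gains −ln(1 − q). At q = 10% the ratio of cumulative hazards is (0.105 + 0.173)/(0.105 + 0.288) = 0.71; at 5% it is 0.224/0.339 = 0.66; at 20% it is 0.396/0.511 = 0.77. Simulated Cox estimates are slightly higher at 5% and 20%, because that model weights by events and many fall in the first four months, when the arms' hazards are nearly equal. The last column supposes that only half the arranged moves are qualifying nursing home admissions.

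| q | Effect (SD) | Power, 80 per arm (t test) | Placement HR, all moves qualify | Placement HR, half qualify |
|---|---|---|---|---|
| 0 | 0.50 | 0.88 | 0.60 | 0.60 |
| 5% | 0.475 | 0.85 | 0.67 | about 0.64 |
| 10% | 0.45 | 0.81 | 0.71–0.72 | 0.67–0.68 |
| 20% | 0.40 | 0.71 | 0.80 | 0.71–0.73 |

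The spread in the last column reflects what is assumed about the moves that do not qualify. With all moves qualifying, log-rank power for placement goes from 0.37 at q = 0 to 0.29, 0.25 and 0.17.

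**The case against.** **Nothing shows that such families enrol.** The Screening Form is not in the documents and may already ask. Families about to move have little reason to join: criterion 6 in 5.2 asks for need, the consent script in 22.1 presents the technology as a way to keep the relative at home, follow-up interviews take about 45 minutes and participation is unpaid. This stands, and it is why the size is given only as a range. It does not close the gap, because no listed criterion would make the answer disqualifying.

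**Zero benefit is the worst case.** Installation is arranged within about two weeks of randomisation, and the caregiver also gets a care plan and a coordination portal, so some benefit could arrive before a move. If affected families lose half the benefit, power (normal approximation) is 0.852 at 10% and 0.812 at 20%. The planned model also adjusts for baseline: with an assumed baseline–outcome correlation of 0.5, power is about 0.90 at q = 10% and 0.83 at 20%, even with no benefit to these families; with 0.3 it is 0.84 and 0.75. This stands.

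**Not every move ends exposure or is an endpoint.** A reader might infer from 5.3 that any move stops the sensors. The text says only that repeat permission is not sought after a move to a care facility. The system is wireless and has been used in residential settings (2.1); reinstallation is neither described nor ruled out. A move to a relative's home is not a nursing home admission. This narrows the placement figures, as the last column of the table shows.

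**Excluding everyone with placement in view would cost too much.** A reader might want applicants and wait-listed families excluded too. Their placement can still be delayed, which is what Hypothesis 3 tests, and removing them would take events from an analysis that has few. This stands and shapes the fix.

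**Conclusion.** The gap is on the face of 5.2 and 9.1, and the direction of its effect, towards no difference, follows from the design. Its size is unknown. The calculations show what an assumed share of families would do; they are not a demonstrated loss.

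A reader might conclude that the trial is underpowered for its primary outcomes on this account. The documents do not support that. The planned sample absorbs about 11% of families with no benefit at all before unadjusted power falls below .80, and more if some benefit survives or baseline adjustment helps. The placement analysis has no such slack, but under the assumed inputs its power is already 0.37 with no such families, so its weakness comes mainly from few events. What these families add there is a bias of the hazard ratio towards 1.

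This is a cheap improvement worth making. It does not threaten the validity of the trial.

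**What to change.** 1. Add one question to the Screening Form, answered before randomisation: is a residential placement, or a move of the person with ADRD out of the current home, already accepted or scheduled, only applied for or wait-listed, or neither?
2. In 5.2 and 9.1, add a criterion for the person with ADRD that excludes only the first group. Reconcile the two wordings of the caregiver's 18-month criterion, and of criterion 6, in the same amendment.
3. Keep families who have only applied or are wait-listed, record that intent before randomisation, and prespecify it in 17.3 as a covariate in the Cox model for nursing home admission.
4. For families already enrolled, use placement intent in the same way if it was collected at baseline. Do not reconstruct it after allocation.

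The cost is one question and an eligibility amendment. A few families become ineligible, and the result then applies to families not already committed to a move.
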